#### 1.8.2 Key Secondary Endpoint with Hypothesis Test: ACPP at 6 Months

The key secondary endpoint is ACPP evaluated at 6 months (Refer to Section 4.2.1 for applicable definitions). Objective: To assess if the 6 months ACPP rates for the COVERA™ Vascular Covered Stent is superior to the primary patency rate for standard PTA, by direct comparison:

**H0:** The (survival) rate  $S_1(t)$  of subjects in the study device treatment group with ACPP through  $t \leq 6$  month post index procedure is less than or equal to that  $S_2(t)$  of PTA treatment group.

**H1:** The (survival) rate  $S_1(t)$  of subjects in the study device treatment group with ACPP through  $t \leq 6$  month post index procedure is greater than that  $S_2(t)$  of PTA treatment group.

That is:

**H0:**  $S_1(t) \leq S_2(t)$ , for  $t \leq 6$  months

**H1:**  $S_1(t) > S_2(t)$ , for  $t \leq 6$  months

Rejection of the null hypothesis will signify that the 6 month ACPP of the COVERA™ Vascular Covered Stent is superior to the 6 month ACPP of standard PTA alone.

A Kaplan-Meier analysis will be used to estimate the survival rate of ACPP in the COVERA™ Vascular Covered Stent and PTA alone groups. A log-rank test will be used to test this hypothesis to determine if the COVERA™ Vascular Covered Stent is superior to PTA alone. The test is successful if the two-sided p-value is less than 0.05 and the result is in favor of the COVERA™ Vascular Covered Stent. In addition to the p-value of the test, the confidence intervals of the rate in each group will be provided. Note that, unless both the primary endpoints, and the TLPP at 12-month endpoint are all successful, the hypothesis for the ACPP at 6-month will be tested for exploratory purpose only.

### 1.8.3 Secondary Endpoints with Descriptive Statistics

The following secondary endpoints will be summarized with descriptive statistics (without formal statistical hypothesis testing) using the MITT population. For categorical variables, summary statistics will include frequency counts and percentages. For continuous variables, summary statistics will include mean, standard deviation, minimum, median, and maximum. Refer to Section 4.2.2 for any applicable definitions.

- TLPP through 30 days, 90 days, 18 months, and 24 months.
- ACPP through 30 days, 90 days, 12 months, 18 months, and 24 months.
- Rate of device and procedure related AEs involving the AV access circuit through 90 days, 6 months, 12 months, 18 months, and 24 months.
- Total Number of AV Access Circuit Reinterventions through 30 days, 90 days, 6 months, 12 months, 18 months, and 24 months.
- Total Number of Target Lesion Reinterventions through 30 days, 90 days, 6 months, 12 months, 18 months, and 24 months.
- IPF evaluated at 30 days, 90 days, 6 months, 12 months, 18 months, and 24 months follow-up.
- IPF-T evaluated at 30 days, 90 days, 6 months, 12 months, 18 months, and 24 months.
- Secondary Patency evaluated through 30 days, 90 days, 6 months, 12 months, 18 months, and 24 months.
- Acute Technical Success.
- Acute Procedure Success (Anatomic and Clinical Success).

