Enrollment:	A total of 280 subjects will be randomized to the study. The primary endpoint analysis will occur when 280 randomized subjects have completed or discontinued before their 6 month follow up. The key secondary endpoint analysis will occur when 280 randomized subjects have completed or discontinued before their 12 month follow up. All subjects will be followed for 24 months post index-procedure.
Investigational Sites:	Up to 35 investigational sites in the United States (US), Europe, and Australia/New Zealand will participate. Treated subjects will be distributed globally with 50-75% of the treated subjects in the U.S.
Study Population:	Male or non-pregnant female $\geq 21$ years of age with an expected lifespan sufficient to allow for completion of all study procedures. Eligible subjects will have a hemodynamically significant stenosis.
Inclusion Criteria	
Clinical Inclusion Criteria
 
 
1. Subject must voluntarily sign and date the Informed Consent Form (ICF) prior to collection of study data or performance of study procedures.
 
2. Subject must be either a male or non-pregnant female <math>\geq 21</math> years of age with an expected lifespan sufficient to allow for completion of all study procedures.
 
3. Subject must be willing to comply with the protocol requirements, including clinical and telephone follow-up.
 
4. Subject must have an upper extremity AV fistula that has undergone at least one successful dialysis session with two-needle cannulation, prior to the index procedure.
 
 
Angiographic Inclusion Criteria
 
 
5. Subject must have angiographic evidence of a stenosis <math>\geq 50\%</math> (by visual estimation) located in the venous outflow of the AV access circuit and present with clinical or hemodynamic evidence of AV fistula dysfunction.
 
6. The target lesion must be <math>\leq 9</math>cm in length. Note: multiple stenoses may exist within the target lesion.
 
7. The reference vessel diameter of the adjacent non-stenotic vein must be between 5.0 and 9.0mm.
 

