## 1.5 Handling of Missing Data

Study endpoints may be missing due to withdrawal of consent, Investigator's decision, LTF and subject death. It is important to minimize missing data by all means and always record the reason for missing. Missing data will be handled as described subsequently.

The primary analysis of the primary effectiveness endpoint is a survival analysis. As a sensitivity analysis, the primary safety endpoint will also be analyzed using survival analysis techniques. In survival analyses, unobserved endpoints are a standard part of the analysis; they are known as "censored observations". As long as the censoring is unrelated to the treatment, this method of handling missing endpoints produces unbiased estimates of the freedom-from-event rates. In addition, as a sensitivity analysis, the primary effectiveness endpoint will be analyzed as a proportion-based binomial rate.

For both primary endpoints, the reason for the censoring of all subjects with missing endpoints will be reported. If there is any indication that the censoring is related to the treatment group, a worst-case analysis may be performed for each primary endpoint, in addition to the standard analysis. In a worst-case analysis, an event will be assumed to have occurred at the time the subject was censored for all such subjects in the Test group. In the Control group, all subjects with missing data will be assumed *not* to have had an event.

In addition, regardless of whether missing data are related to the study intervention, a tipping-point analysis will also be performed, in which assumptions about missing data are varied from worst-case to best-case to examine at what point the missing data would alter the results of the analysis.

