### 1) Key Secondary Endpoint – TLPP at 12 months:

- Assumptions:
  - TLPP rate through 12 months for the study device treated subjects is 55%;
  - TLPP rate through 12 months for the PTA only treated subjects is 33%;
  - Allocation ratio: 1:1;
  - Attrition (drop-out) rate (by 12 months) = 15%
  - The Type 1 error,  $\alpha = 0.025$  (one-sided); and
  - The Type 2 error,  $\beta = 0.10$  (Power =  $1 - \beta = 90\%$ ).
- Sample Size:
  - 280 randomized subjects [238 evaluable] will give 90% power with one-sided type I error = 0.025.

2) Primary Effectiveness Endpoint – TLPP at 6 months:

- Assumptions:
  - TLPP rate through 6 months for the study device treated subjects is 73%;
  - TLPP rate through 6 months for the PTA only treated subjects is 50%;
  - Allocation ratio: 1:1;
  - Attrition (drop-out) rate (by 6 months) = 10%
  - The Type 1 error,  $\alpha = 0.025$  (one-sided); and
  - The Type 2 error,  $\beta = 0.10$  (Power =  $1 - \beta = 95\%$ ).
- Sample Size:
  - 280 randomized subjects [252 evaluable] will give 95% power with one-sided type I error = 0.025.

3) Primary Safety Endpoint – Safety at 30 days:

- Assumptions:
  - The primary safety rate through 30 days in the study device treated subjects is 95%;
  - The primary safety rate through 30 days in the PTA only treated subjects is 95%;
  - Non-inferiority margin  $\delta = 10\%$ ;
  - Allocation ratio: 1:1;
  - Attrition rate (by day 30) = 5%; and
  - The Type 1 error,  $\alpha = 0.025$  (one-sided).
- Sample Size:
  - 280 randomized subjects [266 evaluable] will give 91% power with one-sided type I error = 0.025.

Hence, the sample size of 280 randomized subjects, allocated 1:1, for 140 subjects in the COVERA™ Vascular Covered Stent arm and 140 subjects in the PTA alone arm, will provide approximately 86% power for the both primary effectiveness and primary safety endpoint. The sample size of 280 randomized subjects, allocated 1:1 for 140 subjects in the COVERA™ Vascular Covered Stent arm and 140 in the PTA alone arm, will provide approximately 90% power for the key secondary endpoint.

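### Reintervention totals through 24 months are summarized by arm with no adjustment for time observed, so unequal loss of subjects or accesses can distort them; low severity, inexpensive to fix

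*Combined protocol and SAP*

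**What the plan says.** Section 1.8.3 lists two repeat-event counts: "Total Number of AV Access Circuit Reinterventions through 30 days, 90 days, 6 months, 12 months, 18 months, and 24 months" and "Total Number of Target Lesion Reinterventions through 30 days, 90 days, 6 months, 12 months, 18 months, and 24 months". On their status it states: "The following secondary endpoints will be summarized with descriptive statistics (without formal statistical hypothesis testing) using the MITT population". The summary for a numeric variable is given as: "For continuous variables, summary statistics will include mean, standard deviation, minimum, median, and maximum". Categorical variables get counts and percentages. The available text gives no time-at-risk denominator, no recurrent-event method, and no rule for when counting ends. For definitions the section says "Refer to Section 4.2.2 for any applicable definitions"; that section is not part of the text available here.

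The Protocol Summary sets the horizon: "All subjects will be followed for 24 months post index-procedure". Section 1.6 gives the nearest dropout assumption, "Attrition (drop-out) rate (by 12 months) = 15" per cent, for both arms together. It gives no figure by arm or at 24 months.

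Section 1.5 opens generally ("Study endpoints may be missing due to withdrawal of consent", followed by investigator decision, loss to follow-up and death). The survival methods, the reporting of censoring reasons and the worst-case analysis that follow are tied to the two primary endpoints. A tipping-point analysis is also promised, without naming these counts. Secondary Patency, IPF and IPF-T are reported at the same six time points as the totals.

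**The concern.** A cumulative count depends on how often reinterventions occur and on how long each subject can contribute them. The tested patency endpoints deal with incomplete follow-up through Kaplan-Meier estimation and the log-rank test. The reintervention counts run over a longer horizon and have no equivalent. In a plain mean, a subject who leaves at month 2 after one reintervention enters the 24-month figure as a 1, just like a subject observed for 24 months who needed only one.

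Randomization does not balance this, because dropout, death and access loss all happen after allocation and may depend on treatment. If one arm loses more subjects or accesses, its total falls for a reason unrelated to how often a working access needs treatment. Figures for two randomized arms set side by side will be read as a comparison even when no test is attached.

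**Working it through.** The plan states no rate, count or power for these endpoints, so there is no figure to reproduce. The check is illustrative. Only the 24-month horizon, the 140 randomized subjects per arm and the attrition figures come from the plan; every other input is an assumption.

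**Model.** Reinterventions occur at a constant rate r per year while the subject is observed with a usable access. Loss is exponential with hazard h. The expected count per subject through T years is r × E(T), with E(T) = (1 − exp(−hT))/h. Gaps below are the excess of the arm with less loss over the arm with more; they do not depend on r.

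**Attrition only, equal in both arms.** Taking 15% per year and extending it to year 2 (an assumption), h = −ln(0.85) = 0.1625.
- T = 1: E = 0.923 of 1 year, a 7.7% undercount.
- T = 2: E = 1.707 of 2 years, a 14.6% undercount.

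The plan's own figures are more front-loaded: 5% by 30 days, 10% by 6 months, 15% by 12 months. With straight lines between them and 30 days taken as one month, the 12-month undercount is (1/12)(2.5%) + (5/12)(7.5%) + (6/12)(12.5%) = 9.6%. Either way it is the same in both arms, so the between-arm gap is zero.

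**Attrition plus unequal abandonment.** Let h = −ln(0.85) − ln(1 − a), where a is assumed yearly abandonment, with r = 1.5 per year in both arms.

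| a, arm with more loss | a, arm with less loss | T | Mean totals | Gap |
|---|---|---|---|---|
| 20% | 10% | 1 year | 1.24 vs 1.32 | 6% |
| 15% | 10% | 2 years | 2.21 vs 2.32 | 5% |
| 20% | 10% | 2 years | 2.09 vs 2.32 | 11% |
| 30% | 10% | 2 years | 1.87 vs 2.32 | 24% |

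**Loss from any cause, set directly at 24 months.** Let h = −ln(1 − L)/2, where L is the proportion lost by 24 months, with r = 1 per year and 140 subjects per arm.

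| L, arm A | L, arm B | Total A | Total B | Gap |
|---|---|---|---|---|
| 15% | 15% | 258 | 258 | 0% |
| 15% | 20% | 258 | 251 | 3% |
| 15% | 30% | 258 | 236 | 10% |
| 15% | 40% | 258 | 219 | 18% |
| 20% | 50% | 251 | 202 | 24% |

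Dividing each total by its own time at risk returns the common true rate in every row of both tables.

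The gap is also the limit for a reversed ranking. With 15% against 30% loss, for example, arm B shows the lower total despite a higher true rate only if that rate exceeds arm A's by less than about 10%.

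**The case against.** The strongest reply is that nothing depends on these endpoints. They carry no test and no success criterion; study success rests on the two primary endpoints, and the tested secondaries are TLPP at 12 months and ACPP at 6 months. This stands, and it keeps the severity low. A reader might infer that the trial's conclusions are biased; the documents do not support that.

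Second, the counting rule is not visible. A reader might infer that the plan stops counting at abandonment, or that it has no rule. Neither can be said, because Section 4.2.2 may define when counting ends, whether a replacement access counts, and who is included at each time point. This stands for abandonment. It does not remove the problem for withdrawal and loss to follow-up, where later events are unobserved under any definition, unless that section also adjusts for exposure.

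Third, Secondary Patency, IPF and IPF-T appear at the same time points. Secondary Patency would probably reveal differential access loss, and IPF may account for time. This is useful partial context, but their definitions are not available here, and they do not change how the totals are summarized.

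Fourth, the between-arm gap comes entirely from assumed differences in loss, and a raw count is a legitimate description of procedures performed. Both statements are right. They argue for keeping the totals and adding to them. Nor does a rate penalize access loss: a fistula abandoned at month 2 with no reintervention contributes zero events.

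**Conclusion.** The point holds as a low-severity improvement. On the available text, reintervention totals through 24 months are summarized by arm without regard to time observed. If attrition is 15% per year and continues into year 2, the mean totals fall short by about 8% at 12 months and 15% at 24 months, equally in both arms. A between-arm distortion needs unequal loss. Under the assumed differences it is about 3% to 24% at 24 months with no true difference in rates, and zero if loss is equal.

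These figures rest on constant rates, exponential loss and loss differences that the plan does not give. A reader might infer that the totals favour the device, or count against it; the documents give no loss by arm, so the direction is unknown. Primary and key secondary conclusions are unaffected.

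**What to change.** In Section 1.8.3 keep the raw totals and add beside them, for each arm and for both reintervention endpoints, one of the following:

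- reinterventions per access-year at risk: events divided by time from index procedure to the earliest of abandonment, death, exit or the time point, with a 95% confidence interval that allows for repeat events within subject (robust variance, or a negative binomial model with log access-time as offset); or
- a mean cumulative count, with death and abandonment as terminal events and exit as censoring.

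The two answer different questions. The rate adjusts for all lost time at risk. The cumulative count corrects for exit only and remains lower where more accesses are lost. State which is intended, and state or cross-refer to the end-of-counting rule. Show total access-time, abandonments and exits by arm in the same table. Settle the choice before summaries by arm exist, so that the denominator cannot appear to be chosen from the results.

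The cost is SAP wording and a little programming; the dates needed are probably already collected for patency and censoring. A rate is less simple to read than a count, averages over any change in rate with time, and does not penalize access loss, so it should be read with Secondary Patency.
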